### 5.2.11 Follow-up of Discontinuations

The site should complete all scheduled safety follow-ups and contact any subject who has prematurely terminated the trial because of an SAE, other type of AE, non-compliance with the protocol, or loss of eligibility, including definite contraindications.

For subjects where the reason for early termination was lost to follow-up or if the subject withdrew informed consent and specified that they do not want to be contacted again and it is documented in the source document, the site will not attempt to obtain further safety information.

For subjects where the reason for early termination is voluntary withdrawal, the site will attempt to contact them for the 6-month follow-up, except if they specified that they do not want to be contacted again and it is documented in the source document.

### 5.2.12 Follow-up and Reporting of Pregnancies

Pregnancy is an exclusion criterion for enrollment in this study, but a subject could potentially become pregnant during her participation. In case of pregnancy and if at least one dose of the study vaccine(s) has been administered, the subject will not be discontinued from the trial and will be followed for safety assessment (and may be followed for immunogenicity assessment, if applicable). However, no additional vaccination will be administered.

All pregnancy cases should be reported if they occurred during the study and during the 6 month follow up period. To report the pregnancy case, the Investigator must fill out an electronic Pregnancy Reporting Form in the Electronic Data Capture (EDC) system and inform the Sponsor within 1 month after identifying a pregnancy case.

Study staff must then maintain contact with the subject to obtain information about the outcome—i.e., details about the delivery and the newborn, or about pregnancy termination—and must update the electronic Pregnancy Reporting Form. This information should be provided to the Sponsor within 1 month of delivery. Additional follow-up visits may be performed according to the local regulations.

Pregnancy itself is not considered an AE, but any complications during pregnancy are to be considered as AEs, and in some cases could be considered SAEs. Spontaneous abortions, fetal death, stillbirth, and congenital anomalies reported in the baby are always considered as SAEs, and the information should be provided to the Global Pharmacovigilance (GPV) Department regardless of when the SAE occurs (e.g., even after the end of the trial).

## 5.3 Modification of the Trial and Protocol

Any amendments to this trial plan and protocol must be discussed with and approved by the Sponsor. If agreement is reached concerning the need for an amendment, it will be produced in writing by the Sponsor, and the amended version of the protocol will replace the earlier version. All substantial amendments e.g., that affect the conduct of the trial or the safety of subjects, require IEC/IRB approval, and must also be forwarded to regulatory authorities.

An administrative amendment to a protocol is one that modifies some administrative or logistical aspect of the trial but does not affect its design or objectives or have an impact on the subjects'

safety. The IECs/IRBs and regulatory authorities must be notified of administrative changes and will provide approval according to local regulations.

The Investigator is responsible for ensuring that changes to an approved trial, during the period for which IEC/IRB approval has already been given, are not initiated without IEC/IRB review and approval, except to eliminate apparent immediate hazards to subjects.

## 5.4 Interruption of the Trial

The trial may be discontinued if new data about the investigational product resulting from this or any other trials become available; or for administrative reasons; or on advice of the Sponsor, the Investigators, and/or the IECs/IRBs. If the trial is prematurely terminated or suspended, the Sponsor shall promptly inform the Investigators, the regulatory authorities, and the IECs/IRBs of the reason for termination or suspension, as specified by the applicable regulatory requirements.

The Investigator shall promptly inform the trial subjects and assure appropriate therapy and/or follow-up for them.

# 6 Vaccines Administered

Subjects will receive the CYD dengue vaccine according to a 3-dose schedule, given 6 months apart, with the first dose of CYD dengue vaccine administered either concomitantly or sequentially with a booster dose of Tdap vaccine (Adacel®).

## 6.1 Identity of the Investigational Products

### 6.1.1 Identity of CYD Dengue Vaccine

|                     |  |
|---------------------|--|
| CYD dengue vaccine: | Live, attenuated, tetravalent dengue virus vaccine |
| Presentation:       | Monodose   |
| Form:               | Powder and solvent for suspension for injection    |
| Dose:               | 0.5 milliliters (mL) of the reconstituted vaccine  |
| Route:              | Subcutaneous (SC) injection                        |
| Batch number:       | To be determined                                   |

#### 6.1.1.1 Composition

Each 0.5 mL dose of reconstituted vaccine contains the following components:

- **Active Ingredients:** 4.5 – 6  $\log_{10}$  cell-culture infectious dose 50% (CCID50) of each live, attenuated, recombinant dengue virus serotype 1, 2, 3, 4
- **Excipients:** essential amino acids, non-essential amino acids, L-arginine chloride, saccharose, D-trehalose dihydrate, D-sorbitol, tris (hydroxymethyl) aminomethane, and urea
- **Solvent:** NaCl 0.4%

### 6.1.1.2 Preparation and Administration

Sanofi Pasteur's CYD dengue vaccine consists of a powder and solvent for suspension for injection and must be stored between +2°C and +8°C.

The vaccine must be removed from the refrigerator, reconstituted with the solvent supplied for this purpose, and used immediately after reconstitution.

The vaccine is to be administered subcutaneously in the deltoid region of the upper arm in a volume of 0.5 mL.

Prior to administration, all study products must be inspected visually for cracks, broken seals, correct label content (see [Section 6.3.1](#)), and extraneous particulate matter and/or discoloration, whenever solution and container permit. If any of these conditions exists, the vaccine must not be administered. Another dose is to be used, and the event is to be reported to the Sponsor.

Subjects must be kept under observation for 30 minutes after each vaccination to ensure their safety, and any reactions during this period will be documented in the eCRF. Appropriate medical equipment and emergency medications, including epinephrine (1:1000), must be available on site in the event of an anaphylactic or other immediate allergic reaction.

If a vial or syringe is accidentally broken and the product spilled out, appropriate disinfection procedures must be used (please refer to the Operating Guidelines and/or trial center's procedures).

### 6.1.1.3 Dose Selection and Timing

#### *Tetraivalent vaccine:*

CYD01 assessed safety and immunogenicity of a single dose of monovalent dengue virus serotype 2 chimeric vaccine which demonstrated a satisfactory immune response to serotype 2 but low seropositivity rates to other serotypes thus confirming the need for a tetravalent vaccine. In CYD04, CYD05, and CYD06 the choice of a tetravalent vaccine against all 4 serotypes was confirmed as assessed by immunogenicity responses in several populations across different age group and with different flavivirus background (FV naïve or immune). Furthermore this was supported by CYD11, whereby several bivalent formulations did not improve the immune response compared to tetravalent formulations.

#### *5 log10 CCID50 per serotype (5555) Formulation:*

The results of an early Phase I study (CYD02) showed that a tetravalent formulation with 4 log10 CCID50 per serotype (2 doses given at 5 to 9 month interval) induced moderate but unbalanced Ab levels against the four serotypes [\(13\)](#). Based on these results, it was decided to evaluate a formulation with a higher virus concentration 5 log10 CCID50 per serotype (5555) and to introduce a third injection. The safety and immunogenicity of the 5555 formulation of CYD dengue vaccine (5 log10 CCID50 per serotype) was thus evaluated in additional Phase I trials, CYD04, CYD05, CYD06, CYD12. The 5555 formulation reliably induced an immune response against all 4 serotypes after 3 injections in various populations.

***Vaccination schedule:***

The schedule was selected based on the results from phase I studies CYD02, CYD04, CYD05, and CYD06 in groups receiving tetravalent vaccine at a 3-injection regimen 0,3/4,12 months in different age groups (children, adolescents, adults), different regions (non-endemic USA and Latin America, and endemic Asia Pacific) and different baseline FV status at baseline. The data from initial Phase I studies demonstrated that increasing the interval between injections was beneficial. Furthermore, the benefit of the third injection in terms of seropositivity rate was more marked in younger children and/or subjects who were FV non-immune at baseline. A potential priming effect was also observed following administration of YF vaccine (CYD06) (14).

The choice of the final 3 dose schedule at 6 month intervals apart of 5555 formulation was based on data from phase II studies, especially CYD12. The 3-dose schedule (0, 3–4, and 12 months) and 2-dose schedule (0 and 8–9 months) were adapted to adjust for the higher immunogenicity that occurred when Dose 2 was delayed, balanced by providing protection as soon as possible. CYD12 was the first phase II study testing the final 5555 formulation with the 3 dose schedule 0, 6, and 12 months demonstrating a satisfactory immune response to all 4 serotypes in FV non-immune subjects. Overall, 3 injections at 0, 6 and 12 months of 5555 formulation led to consistent immune response against all serotypes in all age groups, regardless of baseline FV status (15).

**6.1.2 Identity of Adacel**

|               |  |
|---------------|--|
| Adacel®:      | Tetanus Toxoid, Reduced Diphtheria Toxoid and Acellular Pertussis Vaccine Adsorbed |
| Form:         | Suspension for injection in a vial   |
| Dose:         | 0.5 mL   |
| Route:        | Intramuscular (IM) injection   |
| Batch number: | Commercial   |

**6.1.2.1 Composition**

Each 0.5 mL dose of vaccine contains the following components:

- Active Ingredients:
  - Tetanus toxoid 5 Lf
  - Diphtheria toxoid 2 Lf
  - Pertussis toxoid 2.5 µg
  - Filamentous Hemagglutinin 5 µg
  - Pertactin 5 µg
  - Fimbriae types 2 and 3 5 µg
- Excipients:
  - aluminum phosphate (adjuvant) 1.5 mg
  - 2-phenoxyethanol 0.6% v/v

### **6.1.2.2 Preparation and Administration**

Sanofi Pasteur's Tdap vaccine consists of a powder and solvent for suspension for injection and must be stored between +2°C and +8°C.

The vaccine must be removed from the refrigerator, reconstituted with the solvent supplied for this purpose, and used immediately after reconstitution.

The Tdap vaccine is to be administered intramuscularly in the deltoid region of the upper arm, on the opposite side (the one who did not receive the CYD dengue vaccine).

Prior to administration, all study products must be inspected visually for cracks, broken seals, correct label content (see [Section 6.3.1](#)), and extraneous particulate matter and/or discoloration, whenever solution and container permit. If any of these conditions exists, the vaccine must not be administered. Another dose is to be used, and the event is to be reported to the Sponsor.

Subjects must be kept under observation for 30 minutes after each vaccination to ensure their safety, and any reactions during this period will be documented in the eCRF. Appropriate medical equipment and emergency medications, including epinephrine (1:1000), must be available on site in the event of an anaphylactic or other immediate allergic reaction.

### **6.1.2.3 Dose Selection and Timing**

The recommended dose will be administered (this should follow the leaflet).

### **6.1.3 Identity of Control Product**

Not applicable.

## **6.2 Identity of Other Product**

Not applicable.

## **6.3 Product Logistics**

### **6.3.1 Labeling and Packaging**

CYD dengue vaccine will be supplied in vials/syringes and will be labeled and packaged according to national regulations. The information on the label will include:

- Study code
- Name of product
- Route of injection (SC)
- Investigational use only statement (for clinical trial use only)
- Storage conditions
- Batch number
- Dose number

- Name of Sponsor
- Expiry date

For Adacel®, a commercial batch will be used, and the manufacturer's packaging will be used and labeled with specific clinical mention according to national regulation.

### **6.3.2 Product Shipment, Storage, and Accountability**

#### **6.3.2.1 Product Shipment**

The Clinical Logistics Coordinator or designee will contact the Investigator or a designee in order to determine the dates and times of delivery of products.

Each vaccine shipment will include a temperature-monitoring device to verify maintenance of the cold chain during transit. On delivery of the product to the site, the person in charge of product receipt will follow the instructions given in the Operating Guidelines, including checking that the cold chain was maintained during shipment (i.e., verification of the temperature recorders). If there is an indication that the cold chain was broken, this person should immediately quarantine the product, alert the Sanofi Pasteur representative, and request authorization from Sanofi Pasteur to use the product.

#### **6.3.2.2 Product Storage**

The Investigator will be personally responsible for product management or will designate a staff member to assume this responsibility.

At the site, products must be kept in a secure place with restricted access and must be protected from light. Vaccines will be stored in a refrigerator at a temperature ranging from +2°C to +8°C. The vaccines must not be frozen. The temperature must be monitored and documented (see the Operating Guidelines) for the entire time that the vaccine is at the trial site. In case of accidental freezing or disruption of the cold chain, vaccines must not be administered and must be quarantined, and the Investigator or authorized designee should contact the Sanofi Pasteur representative for further instructions.

#### **6.3.2.3 Product Accountability**

The person in charge of product management at the site will maintain records of product delivery to the trial site, product inventory at the site, the dose(s) given to each subject, and the disposal of or return to the Sponsor of unused doses.

The necessary information on the product labels is to be entered into the source document and the eCRF. If applicable, information may also be entered into the subject's vaccination card.

The Sponsor's monitoring staff will verify the trial site's product accountability records against the record of administered doses in the eCRF.

In case of any expected or potential shortage of product during the trial, the Investigator or an authorized designee should alert the Sanofi Pasteur representative as soon as possible, so that a shipment of extra doses can be arranged.

### **6.3.3 Replacement Doses**

If a replacement dose is required (e.g., because the syringe broke or particulate matter was observed in the syringe), the site personnel must follow the instructions given in the Operating Guidelines.

### **6.3.4 Disposal of Unused Products**

Unused or wasted products will be either disposed of or returned to the Sponsor in accordance with the instructions in the Operating Guidelines. Product accountability will be verified throughout the trial period.

### **6.3.5 Recall of Products**

If the Sponsor makes a decision to launch a retrieval procedure, the Investigator(s) will be informed of what needs to be done.

## **6.4 Blinding and Code-breaking Procedures**

The study CYD66 will be an open-labeled study, no blinding is required.

## **6.5 Randomization and Allocation Procedures**

Subjects will be randomized in a 1:1 ratio into Group 1 or Group 2. Stratification according to age will be applied (9 to 11 years, 12 to 17 years, 18 to 45 years and 46 to 60 years) to balance the potential difference in terms of booster response by age group for the pertussis antigens (PT, FHA, PRN and FIM2+3).

The full detailed procedures for randomization are described in the Operating Guidelines.

Subject numbers will be 8 digits long, with a 3-digit center identifier and a 5-digit subject identifier. For example, Subject 001-00001 is the first subject enrolled in center number 1 and Subject 002-00001 is the first subject enrolled in center number 2.

Subject numbers will be an 8-digit string, consisting of a 3-digit study center identifier and a 5-digit subject identifier. The 5-digit subject identifier will correspond to the age group (the first digit will be used to identify the age group, with “0” for subjects aged 9 to 11 years, “1” for subjects aged 12 to 17 years, “2” for subjects aged 18 to 45 years, and “3” for subjects aged 46 to 60 years) and to chronological order of enrollment in the center. Subject identifier will be:

- From 00001 to 09999 for subjects aged 9 months through 11 years
- From 10001 to 19999 for subjects aged 12 years through 17 years
- From 20001 to 29999 for subjects aged 18 years through 45 years
- From 30001 to 39999 for subjects aged 46 years through 60 years

For example, Subject 001-10001 is the first subject in the 12-17 year-old age group enrolled in the study center number 1 and Subject 002-20001 is the first subject from the 18-45 year-old age group enrolled in the study center number 2.

Subject numbers should not be reassigned for any reason.

The Statistical Platform of the Sponsor will provide scratchable randomization lists (one per site). These lists will mention the randomization number of the subject and the corresponding study group covered by a silver-colored patch. After subject number allocation to a subject, the Investigator will scratch off the list to know the study group. Once scratched, each randomization line will be dated and signed by the Investigator or the sub-Investigator in charge of administering the study vaccine(s).

Each subject will be vaccinated with the product(s) corresponding to the group mentioned on the randomization list. If the dose initially taken for the vaccination is broken or cannot be used, the Investigator will take another dose of the same vaccine.

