### 5.1.4 Visit Procedures

#### Visit 1 (Day 0): Inclusion, Randomization, and Vaccination

The Investigator or designated study personnel will:

- 1) Give the subject's parent/legally acceptable representative information about the trial, obtain written informed consent (ICF and AF when applicable), and give him/her a signed copy.
- 2) Obtain significant medical history about the subject and history of dengue infection/vaccination.
- 3) Collect demographic data.
- 4) Check concomitant medications and record every reportable medication ongoing at the time of vaccination.
- 5) Check inclusion and exclusion criteria for eligibility.
- 6) Allocate a subject number to the subject.
- 7) Scratch-off the randomization list to obtain the group allocation, and sign it.
- 8) Perform a physical examination
- 9) Record the subject's axillary temperature (Group 2).
- 10) For female subjects of childbearing potentiala, perform a urine pregnancy test (Group 2).

a To be considered of non-childbearing potential, a female must be pre-menarche or post-menopausal for at least 1 year, surgically sterile, or using an effective method of contraception or abstinence from at least 4 weeks prior to vaccination and until at least 4 weeks after vaccination.

- 11) Obtain blood samplea from subjects in Group 2 (see [Section 7.1](#) for detailed instructions regarding the handling of blood samples). Blood is to be taken from the limb opposite to the one that will be used for vaccination.
- 12) Review temporary and definitive contraindications to vaccination.
- 13) Inject Tdap vaccine to subjects from Group 2.
- 14) Keep the subject from Group 2 under observation for 30 minutes, and record any immediate AE in the source document (Group 2).
- 15) Record the date of injection, the site and side of injection and the route of administration, as well as the dose number of the vaccine (Group 2).
- 16) Give the subject or parent/legally acceptable representative of subjects in Group 2 a diary card (DC), a thermometer, and a ruler, and go over the instructions for their use. Subjects from Group 1, who will not be vaccinated at V01, will receive a DC for the collection of SAE only.
- 17) Remind the subject or parent/legally acceptable representative to bring back the DC when they return for Visit 2 at a specified date and time.
- 18) Remind the subject or parent/legally acceptable representative to notify the site in case of an SAE.

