5.1.1 Hypotheses and Statistical Methods for Primary Objectives

5.1.1.1 Hypotheses

Non-inferiority on Tdap vaccine

The objective is to demonstrate that the humoral immune response to the Tdap booster dose administered concomitantly with the first dose of CYD dengue vaccine is non-inferior to the humoral immune response to the Tdap booster dose administered alone 28 days before the first dose of CYD dengue vaccine.

Individual hypotheses on Tdap response for each antigen:

A non-inferiority testing approach will be used to compare geometric mean concentrations (GMCs) for PT, FHA, PRN, FIM2+3, 28 days after the booster dose of Tdap, for each antigen “i” based on the following individual hypotheses:

$$H_0^i: GMC_{Group1}^i / GMC_{Group2}^i \leq \frac{1}{\delta} \Leftrightarrow \log_{10}(GMC_{Group1}^i) - \log_{10}(GMC_{Group2}^i) \leq -\log_{10}(\delta)$$

$$H_1^i: GMC_{Group1}^i / GMC_{Group2}^i > \frac{1}{\delta} \Leftrightarrow \log_{10}(GMC_{Group1}^i) - \log_{10}(GMC_{Group2}^i) > -\log_{10}(\delta)$$

with:

i, antigen {PT, FHA, PRN, FIM 2+3}.

δ , non-inferiority limit is set at 1.5, i.e., 0.176 ($=\log_{10} [1.5]$), for each antigen “i”.

Non-inferiority for antigen “i” will be demonstrated if the lower bound of the 2-sided 95% confidence interval (CI) is greater than δ ($\alpha=2.5\%$ one-sided). For each of the 4 antigens, the statistical methodology will be based on the use of the age-stratified two-sided 95% CI of the ratio of GMCs between groups. The age-stratified CI will be calculated using an analysis of variance (ANOVA) model (type II analysis) of \log_{10} -transformed titers. The age groups (9 to 11 years, 12 to 17 years, 18 to 45 years and 46 to 60 years) will be used as the stratifying factor in the model.

Additionally, a non-inferiority testing approach will be used to compare seroprotection rates of T and D, 28 days after the booster dose of Tdap vaccine. Seroprotection is defined as anti-D and anti-T Ab concentration superior to 0.1 IU/mL.

The individual tested hypotheses for the antigen “i” will be as follows:

$$H_0^i: P_{Group1}^i - P_{Group2}^i \leq -\delta$$

$$H_1^i: P_{Group1}^i - P_{Group2}^i > -\delta$$

with:

i, antigen {T, D}

δ , non-inferiority limit is set at 10% for both T and D.

Non-inferiority for antigen “i” will be demonstrated if the lower bound of the 2-sided 95% CI is greater than $-\delta$.

Global hypotheses for non-inferiority on Tdap response:

The global hypotheses are:

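### Randomisation lists are issued per site within an age-stratified design, but the primary pertussis model has age only and the primary dengue titre comparison has neither site nor age

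*Protocol*

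**What the plan says.** **Allocation.** Protocol 6.5 sets a 1:1 ratio, stratified on four age groups (9-11, 12-17, 18-45 and 46-60 years), and continues: "The Statistical Platform of the Sponsor will provide scratchable randomization lists (one per site". Protocol section 3 expects about four centres. On each list the group is hidden, with "the corresponding study group covered by a silver-colored patch". The rule for opening a line is: "After subject number allocation to a subject, the Investigator will scratch off the list to know the study group". Afterwards "each randomization line will be dated and signed by the Investigator or the sub-Investigator in charge of administering the study vaccine(s". At Visit 1 (Protocol 5.1.4) the instruction "Scratch-off the randomization list to obtain the group allocation, and sign it" is step 7, after consent, the eligibility check and numbering. Protocol 6.4 adds: "The study CYD66 will be an open-labeled study, no blinding is required". Block size appears in neither document; Protocol 6.5 says "The full detailed procedures for randomization are described in the Operating Guidelines".

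**Analysis.** In SAP 5.1.1.1, as in Protocol 12.1.1.1, the age groups "will be used as the stratifying factor in the model" for the four pertussis GMCs, and no other stratum is named. For the dengue GMTs, Protocol 12.1.1.2 and SAP 5.1.1.2 specify a normal-approximation interval for the difference in mean log10 titre, with no covariate. Tetanus and diphtheria seroprotection use an unstratified Wilson/Newcombe interval. Site is in none of these analyses.

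**The concern.** An analysis should normally respect the groups within which subjects were allocated. Here each site works from its own list and age is the declared stratification factor, yet site is absent from every primary analysis, and age is absent from the dengue comparison.

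When allocation is balanced within a factor that predicts antibody level, variation due to that factor largely cancels from the group difference. If the factor is left out of the model, the same variation stays in the residual SD, so the interval is wider than the design warrants. That matters here for two reasons. All ten primary comparisons must succeed together, and SAP 5.7 allows testing at 510 evaluable subjects, where the plan's own global power is only 80%.

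**Working it through.** **1. Inputs.** One-sided alpha is 0.025. The margins are 0.176 log10 (pertussis) and 0.301 log10 (dengue). SDs are PT 0.4, FHA 0.4, PRN 0.5, FIM2+3 0.6 and serotypes 1-4 1.0, 0.8, 0.8, 0.7 (Protocol 12.5; SAP 5.5). Evaluable numbers are 309 or 255 per group (Protocol Table 12.1; SAP Table 5.4). The share of variance due to site, s, is not in the documents; I assume 5-10%. I take the stated SDs as total SDs.

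**2. The plan's own figures.** Noncentral t, with global power as the product of the individual powers, which treats the endpoints as independent:

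| | 309 per group | 255 per group |
|---|---|---|
| PRN | 99.2% | 97.8% |
| FIM2+3 | 95.4% | 91.1% |
| Serotype 1 | 96.2% | 92.4% |
| Global | 90.3% (stated 90%) | 80.1% (stated 80%) |

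The tabulated powers reproduce. The normal approximation used below gives 91.2% and 92.5% for FIM2+3 and serotype 1 at 255 per group, and 80.3% globally.

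**3. Power with site in the model, 255 per group.** Power = Phi(margin / (SD x sqrt(1-s) x sqrt(2/255)) - 1.96), with sqrt(2/255) = 0.0886.

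- Serotype 1: 0.301/0.0886 = 3.399 at s = 0. Dividing by sqrt(0.95) gives 3.487, and by sqrt(0.90) gives 3.583. Power is 92.5%, 93.7% and 94.8%.
- FIM2+3: 0.176/(0.6 x 0.0886) = 3.312, then 3.398 and 3.491. Power is 91.2%, 92.5% and 93.7%.
- Global, with the same s for all eight GMC/GMT comparisons (noncentral t): 80.1%, 83.3% and 86.3%. Tetanus and diphtheria are above 99.9% and do not affect it.

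**4. How much of that is due to the model term.** Step 3 compares with the tabulated power. If allocation is balanced within site, the unadjusted analysis already does somewhat better than tabulated: Phi((margin/(SD x sqrt(2/255)) - 1.96)/sqrt(1-s)). For serotype 1 this is Phi(1.439/sqrt(1-s)), or 93.0% at 5% and 93.5% at 10%. For FIM2+3 it is Phi(1.352/sqrt(1-s)), or 91.7% and 92.3%. The corresponding products over the eight comparisons are 81.8% and 83.3%, against 83.5% and 86.5% with site included (normal approximation). Under balance, then, the term itself is worth about 1.7 to 3.2 points of global power; the rest of the rise comes from the balance.

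**5. False non-inferiority.** Simulation with the true difference at the 0.301 margin, SD 1.0, 510 subjects, four equal sites, four age strata, assumed blocks of 4 within site and age, and 4,000 runs (Monte Carlo SE about 0.25 points):

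| Site share | Site omitted | Site included |
|---|---|---|
| 0% | 2.3% | 2.2% |
| 5% | 2.4% | 2.7% |
| 10% | 2.0% | 2.6% |
| 20% | 1.4% | 2.4% |

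Theory agrees: Phi(-1.96/sqrt(1-s)) gives 2.2%, 1.9% and 1.4% at 5%, 10% and 20%. Omitting site is conservative.

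**6. At the larger sample.** SAP section 1 reports 629 baseline-seropositive subjects among the 676 who received dengue dose 1. Evaluable numbers could therefore be nearer 309 per group if few are lost to other exclusions. There, noncentral t gives 96.2% rising to 96.9-97.6% for serotype 1 and 95.4% rising to 96.2-97.0% for FIM2+3. The gain is smaller.

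**7. Degrees of freedom.** With 510 subjects and four sites, residual df fall from 505 to 502 (pertussis) and from 508 to 502 (dengue, with site and age added). The critical t is 1.965 throughout.

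**The case against.** **On the analysis.** Site is not a declared stratification factor; age is, with a stated reason concerning the pertussis antigens. The gain rests on a variance share that the documents do not give, and omission errs on the safe side. All of this stands, and it makes the point one of precision, not validity. Still, lists were issued by site, the term costs almost nothing, and the dengue comparison leaves out even the declared factor.

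**A stronger reading: concealment failed.** A reader might infer from open arms and a site-held list that staff could uncover or guess the next assignment. Uncovering a line early would breach the protocol: the group is under a patch, scratching follows numbering, each opened line is dated and signed, and subject numbers run chronologically and are not reassigned. These controls make early opening detectable, though not impossible. Guessing depends on blocking that neither document describes. With fixed blocks of 2, 4, 6 or 8 known to staff, a best guess would be right 75%, 71%, 68% or 67% of the time, against 50% by chance. With unrestricted randomisation, earlier assignments tell nothing.

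One can also calculate that a selection shift of 0.02 or 0.05 log10 in FIM2+3 would raise one-sided error from 2.5% to Phi(-1.96 + 0.02/0.0531) = 5.7%, or to 15.4% at 0.05 (SE = 0.6 x 0.0886 = 0.0531). Neither shift has a source in the documents, so neither figure estimates anything about this trial.

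**One list per site against four age strata.** This is not a contradiction. Subject numbers are coded by age group within centre, and one site list can carry four age sections.

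**Conclusion.** The primary GMC and GMT analyses do not follow the allocation structure: site is missing from both, and age from the dengue comparison. With allocation balanced within site, the consequence is intervals that are too wide and a modest loss of power. Relative to the plan's tabulated values at 255 per group, site adjustment brings about 1 to 2.5 points on the two weakest endpoints and 3 to 6 points globally. Part of that would come from within-site balance even without the term.

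These sizes depend on the assumed 5-10% site share, applied equally to all eight comparisons, and on independence between endpoints. I have not quantified the gain from age in the dengue model, since the documents give no basis for its size.

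The documents do not support saying that false non-inferiority is inflated or that allocation was compromised. The site-held list in an open-label trial gives weaker but auditable concealment. A site term would not remove selection bias if there were any.

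**What to change.** **SAP 5.1.1.** Add site as a main effect to the ANOVA for PT, FHA, PRN and FIM2+3, beside group and age group. Replace the unadjusted dengue GMT difference with a linear model of log10 titre on group, site and age group, and take the two-sided 95% CI for the group effect from it. Amend the normal-approximation wording in SAP 5.1.1.2 to match. Keep the margins, the all-endpoints rule and the threshold of 510 evaluable subjects. The seroprotection intervals can stay as they are, since their power is already above 99.9%.

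Record the change before antibody results are seen by group. If they have been seen, report it as a sensitivity analysis beside the planned one.

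**Secondary check.** List the dated scratch lines against subject-number order and consent dates, and state the block size and list structure from the Operating Guidelines in the study report.

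**Cost.** Three degrees of freedom for site with four centres, three more for age in the dengue model, and one listing from records that the protocol already requires. Changing the allocation method in Protocol 6.5 would not affect this trial, because enrolment is complete and the sponsor has ended the study (SAP section 1 and 3.1).
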